3. LIST OF ABBREVIATIONS AND DEFINITIONS OF TERMS

Table 2: Abbreviations and Specialist Terms

Abbreviation or Specialist Term	Explanation
ADA	Anti-drug antibody
AE	Adverse event
ALT	Alanine aminotransferase
AST	Aspartate aminotransferase
BB	Biceps brachii
CK	Creatine kinase
CRF	Case report form
CTX	C-terminal collagen crosslinks
DLT	Dose limiting toxicity
DUX4	Double homeobox protein 4
ECG	Electrocardiogram
EMG	Electromyography
FDA	Food and Drug Administration
FSHD	Facioscapulohumeral muscular dystrophy
FSHD-HI	Facioscapulohumeral muscular dystrophy-health index
FST	Follistatin
GCP	Good clinical practice
GDF8	Growth and differentiation factor 8
IB	Investigator's brochure
ICF	Informed consent form
ICH	International Council for Harmonisation
IEC	Independent ethics committee
IgG2	Immunoglobulin G2
IM	Intramuscular
IP	Investigational product
IRB	Institutional review board
MMT	Manual muscle testing
MRC	Medical Research Council
MRI	Magnetic resonance imaging
MTD	Maximum tolerated dose

Abbreviation or Specialist Term	Explanation
NCI-CTCAE	National Cancer Institute-Common Terminology Criteria for Adverse Events
PD	Pharmacodynamic
PK	Pharmacokinetic
PUL	Performance of the upper limb
QMT	Quantitative muscle testing
RF	Rectus femoris
SAE	Serious adverse event
SD	Standard deviation
SRT	Safety review team
SUSAR	Suspected unexpected serious adverse reaction
TA	Tibialis anterior
TGF- β	Transforming growth factor beta
ULN	Upper limit of normal

4. PROTOCOL SYNOPSIS

Name of Sponsor/Company: Acceleron Pharma Inc., [name]
Name of Investigational Product: ACE-083
Name of Active Ingredient: ACE-083 is a recombinant fusion protein consisting of a modified form of human follistatin linked to a human IgG2 Fc domain.
Title of Study: A Phase 2 Randomized, Double-Blind, Placebo-Controlled Study of ACE-083 in Patients with Facioscapulohumeral Muscular Dystrophy
Study Centers: Approximately 30 centers
Phase of Development: 2
Objectives
Part 1
Primary:

• To evaluate the safety and tolerability of ACE-083 in patients with facioscapulohumeral muscular dystrophy (FSHD)
Secondary:

• To determine the recommended dose level(s) of ACE-083 for Part 2• To evaluate change in muscle volume and intramuscular fat fraction of the injected muscle• To evaluate change in strength of the injected muscle• To estimate the systemic exposure of ACE-083 when administered as a local muscle injection
Exploratory:

• To evaluate changes in motor function related to the injected muscle• To evaluate changes in patient-reported measures of FSHD-health index (FSHD-HI) total score and subscale scores
Part 2
Primary:

• To determine whether treatment with ACE-083 increases total muscle volume of the injected muscle in patients with FSHD
Secondary:

• To determine whether treatment with ACE-083 decreases intramuscular fat fraction of the injected muscle• To determine whether treatment with ACE-083 increases strength of the injected muscle• To determine whether treatment with ACE-083 improves motor function (e.g., six minute walk test distance, performance of upper limb [PUL] mid-level/elbow dimension assessment) related to the injected muscle

- To evaluate changes in patient-reported measures of FSHD-HI total score and subscale scores
- To evaluate the safety and tolerability of ACE-083
- To estimate the systemic exposure of ACE-083 when administered as a local muscle injection

Exploratory (Part 2, open-label):

- To assess the effect of treatment with ACE-083 on motor function as measured by the 100-meter timed test (tibialis anterior groups) or PUL high level/shoulder dimension assessment (biceps brachii groups)

Methodology

This is a multicenter, Phase 2 study to evaluate the safety, tolerability, pharmacodynamics (PD), efficacy, and pharmacokinetics (PK) of ACE-083 in patients with FSHD, to be conducted in two parts. Part 1 is open-label, dose-escalation (3 months) and Part 2 is randomized, double-blind, placebo-controlled (6 months) followed by an open-label extension (6 months). Patients who have signed the informed consent form (ICF) and meet the eligibility criteria will be enrolled into the study.

Part 1 (dose escalation, open-label)

Part 1 will consist of up to 6 cohorts of patients and will evaluate multiple ascending dose levels of ACE-083 in either the tibialis anterior (TA) or biceps brachii (BB) muscle. Patients in each cohort will be enrolled in a 1-month screening period before beginning treatment.

Cohorts 1a and 1b will be treated in parallel. The dose level in Cohort 1a will be 150 mg (3 mL) administered by multiple injections unilaterally into the TA muscle, once every 3 weeks for up to 5 doses. Patients in Cohort 1b will be similarly treated in the BB muscle. The estimated tissue exposure of ACE-083 (mg/g muscle) is expected to be similar for the TA and the BB, as the two muscles are relatively similar in size.

For Cohorts 2a and 2b, the decision to enroll patients and the dose levels that will be administered will be based upon Safety Review Team (SRT) review of safety and, if necessary, imaging data collected in prior cohorts. The planned dose level for Cohorts 2a and 2b is 200 mg, with a maximum possible dose level of 250 mg, to be selected following SRT review of data from prior cohorts.

For Cohorts 3a and 3b, the decision to enroll patients, dose level (maximum 250 mg), muscle tested (TA and/or BB), and unilateral or bilateral dosing will be based upon SRT review of safety and imaging data collected in prior cohorts.

The SRT will meet to review data for each cohort when at least 4 patients within a cohort have completed their Day 43 visit (SRT meetings for “a” and “b” cohorts can occur separately or together, depending on recruitment). The SRT may recommend one or more of the following: treatment of the remaining patients at the current dose level; escalation to a higher dose level for the next cohort; an intermediate (lower) dose level; or no treatment of additional patients or cohorts. Recommendations made by the SRT may be relevant to both the TA and BB or specific to one or the other muscle, as safety findings and dose escalation may be specific to each muscle.

Part 2 (randomized, double-blind, placebo-controlled, with open-label extension)

Prior to the initiation of Part 2, a review of safety and efficacy data from Part 1 will be conducted to determine whether cohorts for one or both muscles will be pursued in Part 2, as well as the recommended dose level for each muscle. A total of up to 56 new patients (28 patients per muscle) may be enrolled and randomized (1:1) to receive either ACE-083 (n=14/muscle) or placebo (n=14/muscle) bilaterally to either the TA or BB muscles (but not both). Patients will receive blinded study drug once every three weeks for approximately 6 months (9 doses).

Patients who complete the double-blind treatment period will immediately roll over to open-label treatment of ACE-083, receiving the same dose of active drug, bilaterally in either the TA or BB muscle, once every three weeks for approximately 6 months (8 doses). In Part 2, the SRT will periodically review blinded safety data for each muscle treated.

Number of Patients (planned)

Up to 36 patients will be enrolled in the dose escalation phase of the study (Part 1) and up to 56 patients (14 active, 14 placebo per muscle) will be enrolled in Part 2, for a total of up to approximately 92 patients.

Diagnosis and Main Criteria for Eligibility**Inclusion Criteria:**

1. Age \geq 18 years
2. Genetically-confirmed FSHD1 or FSHD2 (or a first-degree relative with genetically confirmed FSHD1 or FSHD2) and clinical findings meeting FSHD criteria
3. Part 1 TA cohorts:
 - a. 6-minute walk distance (6MWD) \geq 150 meters (without a brace)
 - b. Left and/or right ankle dorsiflexion Medical Research Council (MRC) manual muscle testing (MMT) grade 3 to 4+, inclusive ([Appendix 3](#))

Note: Contralateral side may be MRC MMT grade 3 to 5

Part 1 BB cohorts:

- a. Left and/or right elbow flexion MRC MMT grade 3 to 4+, inclusive ([Appendix 3](#))

Note: Contralateral side may be any MRC MMT grade

Part 2 TA cohorts:

- a. 6MWD \geq 150 and \leq 500 meters (without a brace); a maximum of 20% of enrolled patients with 6MWD \geq 450 meters will be included
- b. Left and right ankle dorsiflexion MRC MMT grade 3 to 4+, inclusive ([Appendix 3](#))

Part 2 BB cohorts:

- a. Left and right elbow flexion MRC MMT grade 3 to 4+, inclusive ([Appendix 3](#))
4. Females of childbearing potential (defined as sexually mature women who have not undergone hysterectomy or bilateral oophorectomy, or are not naturally postmenopausal \geq 24 consecutive months) must have negative urine pregnancy test prior to enrollment and use highly effective birth control methods (abstinence, oral contraceptives, barrier method with spermicide, or surgical sterilization) during study participation and for 8 weeks following the last dose of ACE-083. Hormonal birth control use must be stable for at least

14 days prior to Day 1. Males must agree to use a condom during any sexual contact with females of childbearing potential while participating in the study and for 8 weeks following the last dose of ACE-083, even if he has undergone a successful vasectomy. Patients must be counseled concerning measures to be used to prevent pregnancy prior to the first dose of ACE-083.

5. Ability to adhere to the study visit schedule/procedures, and to understand and comply with protocol requirements
6. Signed written informed consent

Exclusion Criteria:

1. Current active malignancy (e.g., remission less than 5 years duration), with the exception of fully excised or treated basal cell carcinoma, cervical carcinoma in-situ, or ≤ 2 squamous cell carcinomas of the skin
2. Symptomatic cardiopulmonary disease, significant functional impairment, or other co-morbidities that in the opinion of the investigator would limit a patient's ability to complete strength and/or functional assessments on study
3. Renal impairment (serum creatinine ≥ 2 times the upper limit of normal [ULN])
4. Aspartate transaminase (AST) and/or alanine transaminase (ALT) ≥ 3 times ULN
5. Increased risk of bleeding (i.e., due to hemophilia, platelet disorders, or use of any anticoagulation/platelet modifying therapies up to 2 weeks prior to Study Day 1; low dose aspirin [≤ 100 mg daily] is permitted)
6. Major surgery within 4 weeks prior to Study Day 1
7. Chronic systemic corticosteroids (≥ 2 weeks) within 4 weeks before Study Day 1 and for duration of study; intra-articular/topical/inhaled therapeutic or physiologic doses of corticosteroids are permitted
8. Androgens or growth hormone within 6 months before Study Day 1 and for duration of study; topical physiologic androgen replacement is permitted
9. Any change in medications potentially affecting muscle strength or function within 4 weeks of Study Day 1 and for duration of study (e.g., creatine, CoQ10, systemic beta-adrenergic agonists)
10. Previous exposure to any investigational agent potentially affecting muscle volume, strength, or function within 5 half-lives of last dose or 4 weeks of Study Day 1 if half-life is unknown, or any prior exposure to ACE-083
11. Significant change in physical activity or exercise (e.g., significant increase or decrease in intensity or frequency) within 8 weeks before Study Day 1 or inability to maintain the baseline level of physical activity throughout the study
12. Any condition that would prevent MRI scanning or compromise the ability to obtain a clear and interpretable scan of the TA or BB muscles, as applicable (e.g., pacemaker, knee/hip replacement, or metallic implants)
13. Known active substance abuse, including alcohol
14. History of sensitivity to protein pharmaceuticals
15. Female that is lactating/breast-feeding

Investigational Product, Dosage, and Mode of Administration

ACE-083 drug product is provided as a lyophilized powder contained in stoppered and sealed glass vials. Each single-use vial will be reconstituted with sterile water and contains 1.2 mL of ACE-083 solution for injection after reconstitution. ACE-083 drug product solution for injection contains ACE-083 at a nominal concentration of 50 mg/mL.

Using electromyography (EMG) or ultrasound guidance, each dose of study drug will be administered into the non-tendinous portion of the TA or BB up to 5 equal-volume injections per muscle. The use of EMG or ultrasound guidance will ensure that viable muscle is present at the injection site. If the degree of atrophy or fibro-fatty infiltration poses administration challenges, injections of ACE-083 should be distributed at least 2 cm apart into viable muscle. Injection site locations as well as measures to avoid adjacent nerves and blood vessels and prevent intravascular injection are outlined in the Investigational Product (IP) Handling Guide.

For unilateral dosing (part 1 only), if disease involvement in the lower leg or upper arm is asymmetric, the side that is weakest should be injected provided the MRC criterion is met. For bilateral dosing in Part 1, if only one side is weak (i.e., contralateral side is MRC grade 5), it is acceptable to enroll the patient and to inject only the weak side. If a patient meets inclusion criteria for both the TA and BB, the investigator will choose one target muscle based on the patient's clinical presentation as well as on cohort availability and ability to complete assessments for muscle volume (MRI), strength, and function.

In Cohorts 1 and 2 of Part 1, each dose will be administered unilaterally into the same targeted muscle, once every 3 weeks for up to 5 doses. For optional Cohort 3, bilateral dosing may be explored (to be determined by SRT), with a maximum absolute dose level of 250 mg/muscle administered bilaterally every 3 weeks for 5 doses.

For Part 2, ACE-083 or placebo (normal saline) will be administered every 3 weeks for approximately 6 months (9 doses). Patients who complete the double-blind treatment period will immediately roll over to open-label treatment of ACE-083, receiving the same dose of active drug, bilaterally in either the TA or BB muscle, once every three weeks for approximately 6 months (8 doses).

The planned dose scheme for Part 1 is below.

Part 1: N=Up to 36 (3-month, dose-escalation, non-randomized, open-label)

Cohort	Muscle	Dose Level ^a	ACE-083 n
1a	Tibialis anterior	150 mg	6
2a	Tibialis anterior	200 mg ^b	6
3a (optional)	Tibialis anterior	TBD ^b	6

^a Injection into muscle once every three weeks

^b Dose levels for Cohorts 2 and 3 to be determined by SRT, not to exceed 250 mg per muscle

Cohort	Muscle	Dose Level ^a	ACE-083 n
1b	Biceps brachii	150 mg	6
2b	Biceps brachii	200 mg ^b	6
3b (optional)	Biceps brachii	TBD ^b	6

The planned dose scheme for Part 2 is below.

Part 2: N=Up to 56^a (6-month, randomized, double-blind, placebo-controlled, with 6-month open-label extension)

6-month, double-blind, placebo-controlled				6-month, open-label extension		
Muscle	Dose Level ^b	ACE-083 n	Placebo n	Muscle	Dose Level ^b	ACE-083 n
Tibialis anterior	TBD ^c	14	14	Tibialis anterior	TBD ^c	28
Biceps brachii	TBD ^c	14	14	Biceps brachii	TBD ^c	28

^a N=14 active, 14 placebo per muscle.

^b Injection into muscle once every three weeks

^c Based on review of Part 1, not to exceed 250 mg per muscle

Individual Dose Modification Rules

For an adverse event (AE, including injection site reaction) of Grade 3 or higher, regardless of relationship to study drug, treatment will be paused and the patient will be monitored weekly. Dosing may resume upon resolution of the AE to \leq Grade 1 or baseline, at the discretion of the investigator. Dose level should be reduced by one level (i.e., from 240 to 200 mg or from 200 to 150 mg) for events related to study drug for the remainder of the study; treatment will be discontinued if event occurred at 150 mg dose.

Duration of Study

Study duration for a patient in Part 1 will be approximately 6 months, including a 1-month screening period, a 3-month treatment period, and a 2-month follow-up period after the last dose. Study duration for a patient in Part 2 will be approximately 15 months, including a 1-month screening period, a 12-month treatment period (6-month double-blind, placebo-controlled and a 6-month open-label extension), and a 2-month follow-up period after the last dose.

If a patient has a positive anti-drug antibody (ADA) result at the last visit, the patient will be asked to return for additional ADA testing approximately every three months, until a negative result is obtained or the result is considered to be stabilized.

Reference Therapy, Dosage, and Mode of Administration

The placebo (control agent) to be used in Part 2 of this study will be sterile normal saline (0.9% sodium chloride for injection). Sterile normal saline will be supplied by the investigational site's pharmacist. The manufacturer's directions for saline storage and handling are to be followed, as are standard clinical practices for ensuring sterility. Saline-filled syringes will be prepared by unblinded study personnel and provided to blinded study personnel for administration.

Safety Assessment:

Dose-Limiting Toxicity (DLT) Definition:

- A serious adverse event (SAE), possibly or probably related to study drug

OR

- An adverse event (AE), injection site reaction, laboratory parameter abnormality, or vital sign abnormality, possibly or probably related to study drug, and either grade ≥ 3 (National Cancer Institute-Common Terminology Criteria for Adverse Events [NCI-CTCAE], Version 4.03) or grade ≥ 2 and considered clinically significant.

Part 1 Dose Escalation Stopping Rules (under SRT review):

Dosing at current levels will continue unless the following condition occurs:

- ≥ 2 DLTs of the same character in a cohort

Safety Review Team (SRT):

An SRT, comprised at minimum of a principal investigator, medical monitor, and an independent neuromuscular specialist, will review all collected safety data when at least 4 patients in a cohort have completed their Day 43 visit.

The SRT will review safety data including but not limited to AEs, laboratory results (including hematology and chemistry), urinalysis results, and vital signs data to assess for DLTs and overall safety of each dose level within each muscle. The SRT may request collection of additional data from currently enrolled patients. Based on review of safety data, the SRT will make one or more of the following recommendations:

- Continue enrollment in current cohorts
- Open next cohort and treat
- Discontinue one or more cohorts
- Begin enrollment into Part 2
- Discontinue the study

SRT recommendations for dose escalation in Part 1 will be based in part upon the dose escalation stopping rules for each muscle. If a stopping rule is met, a lower intermediate dose may be recommended or the previous dose level will be considered the maximally tolerated dose (MTD). The SRT may also decide to cease enrollment in the presence of AEs that do not meet dose stopping rules if the nature of these AEs is deemed a significant risk to patients in a given cohort. In addition, the SRT will recommend a dose level for each muscle in Part 2. In Part 2, the SRT will periodically review blinded safety data for each muscle treated. Further details on the role of the SRT during Part 2 are included in the SRT Guidelines.

Assessments for Evaluation:

Safety: AEs, injection site reactions, concomitant medications, clinical laboratory tests (including hematology, chemistry, and ADA), urinalysis, vital signs, and physical examination findings.

Pharmacokinetics: ACE-083 serum concentrations

Pharmacodynamics: selected laboratory biomarkers (e.g., total testosterone, estradiol, serum C-terminal collagen crosslinks [CTX])

Efficacy:

Muscle volume: Muscle volume and intramuscular fat fraction in the TA and BB by MRI

Muscle strength: Muscle strength (maximum voluntary isometric contraction) of ankle dorsiflexion and elbow flexion measured by quantitative muscle testing (by handheld dynamometer [Part 1 and Part 2] and at selected sites by fixed system [Part 1])

Motor function tests: TA muscle function by 10-meter walk/run, 100-meter timed test (Part 2, open-label), 4-stair climb, 6-minute walk test, and gait analysis; BB muscle function by performance of the upper limb (PUL) testing ([Appendix 4](#)) and by upper extremity-specific FSHD-HI subscale scores

Patient-reported disease burden and health-related quality of life: Patient-reported measures of quality of life and self-assessments of disease burden by the FSHD-HI total score and subscale scores

Statistical Methods:

Sample Size Calculation:

Part 1

There is no formal sample size calculation for Part 1. Six patients in each cohort will provide sufficient data to evaluate safety and a preliminary assessment of changes in muscle volume and muscle strength.

Part 2

The sample size calculation for Part 2 is based upon the percent change from baseline in total muscle volume of the injected TA muscle 3 weeks after the last dose. A 10% difference between ACE-083-treated and placebo groups in the percent change in total muscle volume from baseline is considered to be clinically meaningful. The standard deviation (SD) is assumed to be approximately 9% for each group, based on preliminary MRI data for the ACE-083-treated side from the initial TA cohort in Part 1. Similar assumptions apply for treatment of the BB muscle.

Assuming a 2-sided type 1 error rate of 0.10, a 10% difference in percent change from baseline between the ACE-083-treated and placebo groups in total muscle volume, a standard deviation of 9% for each group, and a 1:1 randomization, 83% power is achieved with a total sample size of n=24 for the TA muscle (12 active, 12 placebo), based on a standard t-test.

In addition, this sample size also provides 83% power to detect a 10% difference in 6MWD, based on a similar estimated SD of 9% and a 2-sided type 1 error rate of 0.1.

In order to account for dropouts (up to 15%), 28 patients will be randomized to study treatment for each muscle (14 active, 14 placebo) to ensure that at least 12 patients per treatment group complete the double-blind treatment period.

Analysis Populations:

Full Analysis Set: Part 1: All patients enrolled in the study and have received at least one dose of study drug. Part 2: All patients randomized in the study

Safety Population: All patients enrolled/randomized in the study who have received at least one dose of study drug (including placebo)

Per Protocol Set: All patients enrolled/randomized in the study, who have received at least one dose of study drug (including placebo) with no major protocol violations and at least one post-baseline efficacy evaluation

Pharmacokinetics Population: All patients who have received at least one dose of study drug and have sufficient PK samples collected and assayed for PK analysis

Statistical Analysis:

Complete details regarding the statistical analyses outlined below will be presented in a separate statistical analysis plan. For statistical analyses involving safety data, these will be done on the safety population. For statistical analyses involving pharmacokinetic data, these will be done on the pharmacokinetics population. For statistical analyses involving efficacy and/or pharmacodynamics data, these will be done using the full analysis set and per protocol set populations.

Part 1: Safety, pharmacodynamic and efficacy data will be summarized by cohort. For each efficacy parameter, the absolute and percent change from baseline in the injected TA or BB and, with the exception of motor function tests and FSHD-HI total score and subscale score data, the raw and percent change from baseline of the treated, untreated, and treated minus untreated TA or BB muscle will be presented over time for patients receiving unilateral dosing of ACE-083.

For efficacy measurements that are collected multiple times during the 1-month screening period, changes observed during this time will serve as the control for each patient. They will be summarized together with post-baseline data.

Part 2: The primary efficacy parameter will be the percent change in total muscle volume from baseline of the injected TA or BB 3 weeks after the last dose of the double-blind treatment period. A repeated measures analysis of covariance model will be used to compare the two treatment groups (ACE-083 and placebo) using a 2-sided 0.10 significance level. If the 3-week post last dose data from the double-blind treatment visit are missing, the last observation will be carried forward. Additional techniques for handling missing data will also be evaluated as sensitivity analyses to the last observation carried forward approach.

Other strength and functional measurements will be tested similarly. Estimates of the effect of ACE-083 and corresponding 90% confidence intervals will be produced.

Where applicable, pooling of patient data may be done within and across Part 1 and Part 2 the details of which will be described in the statistical analysis plan. Pooling by the estimated local dose of ACE-083 in the injected muscle (i.e., mg ACE-083/g muscle) may also be performed.

AEs will be coded using the Medical Dictionary for Regulatory Activities. Incidence of treatment-emergent AEs will be presented by system organ class and preferred term. AE incidence rates will be described by cohort and by muscle with and without regard to causality. The frequency of occurrence of overall toxicity, categorized by toxicity grades (NCI-CTCAE, Version 4.03) will be summarized. Change from baseline in clinical laboratory parameters and vital signs will be summarized across time. Shift tables will be presented for selected laboratory parameters, and vital signs. Physical examination results will be presented in listings.

Pharmacodynamic data will be listed and summarized by cohort for each scheduled time.

Listings of individual patient serum ACE-083 concentrations, actual blood sampling times, and PK parameters including graphs of concentration versus time will be prepared by dose level. PK

parameters of ACE-083 will be determined using the standard non-compartmental method. Descriptive statistics of PK parameters will be summarized by cohort.

The results of ADA testing for ACE-083 versus time as well as results following further characterization of positive ADA samples will also be presented. Exploratory analysis will be performed on the potential effect of ADA on ACE-083 PK exposure if ADA tests are determined to be positive.

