^a Injection into muscle once every three weeks^b Dose level for Cohorts 2 and 3 to be determined by SRT, not to exceed 250 mg per muscle**Part 2: N=Up to 56^a (6-month, randomized, double-blind, placebo-controlled and 6-month open-label extension)**

6-month, double-blind, placebo-controlled			
Muscle	Dose Level ^b	ACE-083 n	Placebo n
Tibialis anterior	TBD ^c	14	14
Biceps brachii	TBD ^c	14	14

6-month open-label extension		
Muscle	Dose Level ^b	ACE-083 n
Tibialis anterior	TBD ^c	28
Biceps brachii	TBD ^c	28

^a N=14 active, 14 placebo per muscle.^b Injection into muscle once every three weeks^c Based on review of Part 1, not to exceed 250 mg per muscle**10.1.1. Individual Dose Modification Rules**

For an adverse event (AE, including injection site reactions) of Grade 3 or higher, regardless of relationship to study drug, treatment will be paused and the patient will be monitored weekly. Dosing may resume upon resolution of the AE to \leq Grade 1 or baseline, and dose level may be reduced to the prior dose level deemed safe by SRT, at the discretion of the investigator. Dose level should be reduced by one level (i.e., from 240 to 200 mg or from 200 to 150 mg) for events related to study drug for the remainder of the study; treatment will be discontinued if event occurred at 150 mg dose. If dosing does not resume within 6 weeks of the last dose given, the patient will be discontinued from treatment.

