10.3. Concomitant Medications

During screening and throughout the study, patients may take stable doses of medications for chronic conditions that are not specifically excluded by the protocol. If there is an immediate clinical need during the study to prescribe a new medication or a new dosage of an existing medication for either a new or chronic condition, concurrent therapy may be administered at the discretion of the investigator. Androgens or growth hormone (topical physiologic androgen replacement is permitted) and any change in medications potentially affecting muscle strength or function (e.g., creatinine, CoQ10, systemic beta-adrenergic agonists) are prohibited. The investigator may consult the medical monitor regarding what constitutes a stable dose or a

chronic condition. Information regarding concomitant medications will be collected beginning at study screening and will include all medications taken within 4 weeks prior to Study Day 1.

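### Exclusion 5 treats anticoagulant and platelet-modifying drugs as a bleeding risk only up to Study Day 1, and nothing in the protocol or SAP tells sites to withhold later injections if one is started on study.

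*Protocol*

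**What the plan says.** The Protocol Synopsis and section 8.2 give the same exclusion 5. Under increased bleeding risk it lists "use of any anticoagulation/platelet modifying therapies up to 2 weeks prior to Study Day 1", with aspirin up to 100 mg daily permitted. Section 8.2 applies the criteria at screening, as a bar to enrollment. Other drug exclusions are carried forward explicitly. Exclusion 8, for example, covers "Androgens or growth hormone within 6 months before Study Day 1 and for duration of study", and exclusions 7 and 9 carry the same extension.

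Dosing is by "up to 5 equal-volume injections per muscle", every 3 weeks. Part 2 is bilateral, with 9 double-blind and 8 open-label doses.

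Three on-study rules bear on the point:

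- Section 10.3 says that "patients may take stable doses of medications for chronic conditions that are not specifically excluded by the protocol". If a new drug or dosage is urgently needed, then "for either a new or chronic condition, concurrent therapy may be administered at the discretion of the investigator". The drugs it prohibits are androgens, growth hormone and changes in muscle-active medication.
- Section 10.1.1 says that for an adverse event "of Grade 3 or higher, regardless of relationship to study drug, treatment will be paused and the patient will be monitored weekly". The condition for restarting concerns the event alone, which must have settled to the patient's starting level or to no worse than Grade 1. A time limit closes the rule: "If dosing does not resume within 6 weeks of the last dose given, the patient will be discontinued from treatment".
- SAP 4.2 counts failure to receive the full planned dose at two or more consecutive visits as a major protocol violation, except for safety dose reductions or feasibility. SAP 4.7.2.2 makes the Per Protocol Set the primary analysis set.

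**The concern.** The protocol itself classes these drugs as a bleeding risk serious enough to refuse entry. The risk comes from needle injection into muscle, and that continues for the whole treatment period, while the restriction stops at the first dose. A patient who starts an anticoagulant at week 4 has the same risk that exclusion 5 was written to avoid. No available text tells the site what to do about the next dose, so the decision falls to each of approximately 30 centers. At stake is the safety of that patient. No effect on the primary endpoint is claimed.

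**Working it through.** **1. Could another rule produce a hold?**

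| Place | What it does | Holds the dose for drug use? |
|---|---|---|
| Exclusion 5 | Restricts entry; ends at Day 1 | No |
| 10.3, first sentence | Can be read as barring stable chronic use of excluded drugs | Gives no dosing instruction |
| 10.3, new medication | Allows it for urgent need; prohibited list omits this class | No |
| 10.1.1 | Pauses for a Grade 3 or higher event; resumes when the event settles | No: a drug given as prophylaxis or for a milder event triggers nothing, and one still being taken does not prevent resumption |
| 9.1, 9.2 | Reasons to stop treatment or leave the study | Not listed |
| 10.2 | Dose-limiting toxicity rules | Act only after a toxicity |
| SAP 4.2 | Major violations | Silent |

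Protocol Table 6 schedules concomitant-medication monitoring at dosing visits, and its footnote 1 puts study procedures before injection. The review point therefore exists; what is missing is an action attached to it.

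**2. Remaining schedule after Day 1.**
- Part 2: 9 + 8 − 1 = 16 doses; 16 × 5 injections × 2 sides = up to 160 per patient. Double-blind only: 8 × 10 = 80.
- Part 1: 5 − 1 = 4 doses; 4 × 5 = 20 unilateral, or 4 × 10 = 40 bilateral.

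These are maxima over the remaining schedule.

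**3. Timing of a hold** (14-day washout, 21-day dosing interval, 42-day limit; days counted from the last dose).
- No delay if the drug stops by day 21 − 14 = 7.
- Still within the limit if it stops by day 42 − 14 = 28; the next dose is then at most 42 − 21 = 21 days late.
- Stopped after day 28, or taken long term: treatment ends.

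The 21 days is per hold. Visit windows run from the previous dose, so repeat holds add up and can move Day 190.

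**4. The plan's own power figure.** Inputs from Protocol 14.3: difference 10%, SD 9%, 12 per arm, two-sided alpha 0.10, t-test. Noncentrality = 10 / (9 × √(1/12 + 1/12)) = 2.72, df = 22. Power = 83.9%, which agrees with the stated 83%. The hold changes none of these inputs.

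**5. Cost in patients.** The documents give no rate of starting these drugs. Assume p = 1%, 2% or 4% in the double-blind period and, as a worst case, that every such patient is lost. Expected loss per arm = 14p; chance of at least one loss = 1 − (1 − p)^14.

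| Assumed p | Expected loss per arm | Chance of at least one |
|---|---|---|
| 1% | 0.14 | 13% |
| 2% | 0.28 | 25% |
| 4% | 0.56 | 44% |

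Ordinary dropout already uses the margin: 15% of 14 is 2.1, which takes an arm from 14 to about 12. A loss from the hold may come on top. With 11 against 12, power is 82.4%.

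**The case against.** The strongest objection is that the absence cannot be proved. Injection technique and administration are delegated to the IP Handling Guide and study procedures to the Study Manual, and a pre-injection bleeding check would sit naturally in either. This stands. A reader might infer that the trial has no such rule anywhere; the finding covers the protocol and SAP text only.

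A second objection is that other safeguards exist: injection-site examinations that look for bruising and bleeding, scheduled platelet counts, periodic review by the Safety Review Team, and adverse events as a reason to stop. These are real, but most act after harm, and a platelet count does not detect anticoagulant use. The first sentence of 10.3 limits chronic use but leaves the dosing decision open.

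A third is that the contrast with exclusions 7 to 9 is weak evidence of an oversight. Exclusions 8 and 9 appear to protect the muscle endpoints, and exclusion 6 (major surgery), also a procedural risk, likewise ends at Day 1. That is fair. A reader might infer that these drugs should simply be banned for the whole study; the contrast does not support that, and a ban on clinically needed therapy would be undesirable. The gap is in the dosing rule.

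Finally, 160 injections might be read as exposure while on the drug. It would be that only for a patient who started just after Day 1 and continued throughout. The documents give neither a start rate nor a bleeding rate, so the safety gain stays unquantified.

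**Conclusion.** The concern holds for the available text. The written rules permit continued injection of a patient whom exclusion 5 would have refused, and the only automatic pause depends on a Grade 3 or higher event. A hold should be added, or cross-referenced if the IP Handling Guide or Study Manual already contains one. The safety benefit has no numerical size. The cost figures rest on assumed start rates of 1% to 4% and on every such patient being lost, which is a worst case because a short hold need lose nobody. On those assumptions an arm loses 0.14 to 0.56 patients on average, possibly beyond the planned dropout. A reader might infer that the gap biases the primary result or undermines the sample size; nothing in the documents supports either.

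**What to change.** Add to Protocol 10.3 and 10.1.1:

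1. At each pre-dose visit, withhold study drug if in the previous 2 weeks the patient has used any therapy covered by exclusion 5, in its existing wording and with aspirin up to 100 mg daily still permitted, or if a bleeding or platelet disorder has been newly diagnosed.
2. Do not stop a clinically needed drug in order to give a dose.
3. Dosing may resume 2 weeks after the drug is stopped.
4. The existing 6-week limit applies to this hold. It needs saying because that limit now stands in a rule about adverse events.

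Keeping exclusion 5's wording leaves eligibility unchanged.

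In SAP 4.2, state that doses withheld for this safety reason are handled like safety dose reductions and are not a major protocol violation. Without that line, a hold across two consecutive visits could remove the patient from the primary analysis set, because the present exemption names reductions and does not mention withheld doses. The separate rule on leaving the study before the Day 43 visit stays as it is.

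The cost is a few sentences in an amendment and one SAP line, with no new visit or test. The downside is that a patient needing long-term therapy loses the remaining doses yet stays in the Per Protocol Set with reduced exposure, and each hold can delay later visits by up to 21 days, with repeat holds accumulating.
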